CCUK	Crohn's & Colitis UK (registered charity supporting people with IBD)
CCOK	Crohn's disease
CRF	Case Report Form
CI	Chief Investigator
CV	Curriculum Vitae
FI	Faecal Incontinence
GCP	Good Clinical Practice
GDPR	General Data Protection Regulation
GP	General Practitioner
HRA	Health Research Authority
IBD	Inflammatory Bowel Disease
IRAS	Integrated Research Application System
KCL	King's College London
LNWH	London North West Healthcare NHS Trust
NHS	National Health Service
NICE	National Institute for Clinical Excellence
NIHR	National Institute for Health Research
NRES	National Research Ethics Service
PCTU	Pragmatic Clinical Trials Unit (Queen Mary, University of London)
PGfAR	Programme Grant for Applied Research
PI	Principal Investigator (local collaborator / lead at each research site)
PIS	Patient Information Sheet
PMG	Programme Management Group
PSC	Programme Steering Committee
PPI	Public and Patient Involvement
QMUL	Queen Mary's University of London
RCT	Randomised Control Trial
REC	Research Ethics Committee
SAEs	Serious Adverse Events
SoA	Statement of Activities
SoE	Schedule of Events
L	

UC

Ulcerative Colitis

STUDY SUMMARY

Short Title	IBD-BOOST: OPTIMISE
Methodology	A multicentre, non-randomised interventional study with 2 elements:
	 Self-completed checklist and postal faecal calprotectin sample
	2. Review of checklist and if necessary review of the patient
	(telephone or clinic visit) by IBD nurse/other suitable trained staff to identify potential 'red flag' symptoms and/or
	active disease and other reversible causes for symptoms of fatigue, pain and urgency in people with Inflammatory
	Bowel Disease, according to a pre-developed algorithm. To manage any causes found according to the clinical
	algorithm. Process evaluation one to one online or
	telephone interviews with staff members carrying out the study for qualitative insights on intervention feasibility.
Research Sites	NHS Trusts:
	 London North West University Hospital NHS Trust (St Mark's Hospital)
	2. St Helens and Knowsley Teaching Hospitals NHS Trust
	(Whiston Hospital or St Helens Hospital)
	 Dorset County Hospital NHS Foundation Trust (Dorset County Hospital)
	4. Barts Health NHS Trust (Royal London Hospital)
Objectives/Aims	To screen patients with Inflammatory Bowel Disease who have
	indicated on a previous survey that they want help for fatigue,
	pain and/or urgency, to determine how many have potential
	medical causes of symptoms and to describe change in symptom scores after addressing those causes identified. To determine the
	feasibility of the IBD symptom checklist and algorithm in clinical
	practice and the costs incurred by the NHS, and additional
	qualitative process evaluation.
Number of	200 patients
Participants/Patients	
Main Inclusion	Inclusion criteria
Criteria	 Diagnosis of IBD (including patients with an ileo-anal pouch or stoma)
	18 years and over
	Lives in UK and attends one of the IBD-BOOST clinical
	sites for routine IBD care
	 Has completed the IBD-BOOST survey (stage 2 of
	Programme Grant) and indicated that they would like further support to help manage their symptoms
	Ability to give informed consent and sufficient command of
	English to understand study documents and procedures will be assumed from response to the previous survey
	Exclusion criteria
L	

	Under 18 years	
Analysis	 Statistical analysis to determine: Proportion of patients with at least one potentially treatable cause for symptom/s (including active IBD disease flare-up). For those receiving any test or intervention for a potentially treatable cause identified by the algorithm: change in symptom scores for fatigue, pain and incontinence will be estimated (at 3 months). Proportion of people completing the checklist who have symptoms but subsequently decline suggested medical test or intervention (such as a blood test or medication). Health economics analysis to estimate (among participants undergoing medical optimisation): IBD-related healthcare use and costs incurred for tests and subsequent interventions (NHS perspective) Change in health-related quality of life (EQ-5D-5L utility) Qualitative analysis of process evaluation interviews with staff members (1 per site) carrying out the study for insights on feasibility and suggested modifications. 	
Proposed Start Date	1 st June 2019	
Proposed End Date	31 st December 2022	
Proposed follow-up end	31 st March 2023	
Study Recruitment Duration	43 months	
Study Total duration	46 months	

ROLES AND RESPONSIBILITIES OF COMMITEES/GROUPS & INDIVIDUALS

The Chief Investigator (CI) ([name]) has overall responsibility for the study.

The Programme Management Group (PMG), includes all co-investigators of the IBD-BOOST programme as well as the research team. The PMG and research team are responsible for the planning, execution, analysis and writing up the project.

Programme Co-investigators

[name]	Queen Mary University of London

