2. OBJECTIVES

2.1 Primary research question:

I. Of those people with IBD who experience fatigue, pain and/or faecal urgency/incontinence and express an interest in intervention for one or more of these symptoms, what proportion have patho-physiological contributors which are potentially medically treatable?

2.2 Secondary research questions:

- I. Is implementing this checklist and algorithm feasible in routine NHS clinical practice?
- II. In patients with symptoms and potentially reversible medical causes do these symptoms change at 3 months after initiating algorithm-led management? Note: the design of this study will not allow inference of causality of symptoms.
- III. In patients starting algorithm-led management, what NHS resources are used during the implementation of the algorithm?
- IV. In patients starting algorithm-led management, what change is observed in healthrelated quality of life (EQ 5D 5L utility)?
- V. What is the experience of nurses implementing the Optimise algorithm and what are their suggestions for any changes to enable future NHS implementation (via qualitative interviews)?

This study also aims to identify and prepare potential participants for a future RCT of an online symptom management intervention. Participants who are not found to have any potentially treatable patho-physiological contributors will be invited to take part in the next stage of the programme, an RCT of an online self-management intervention. Participants who are identified as having potentially treatable contributors but have not experienced resolution of symptoms after three months of following the algorithm and want further help with symptoms will also be invited to the RCT.

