6.2 Outcome measures

Primary outcome measures

Proportion of participants with any of the following detected via the checklist, faecal calprotectin test or by the nurse/clinician following the algorithm (recorded on the Checklist, Appendix 4 & Optimisation CRF, Appendix 5):

- "Red flags" on checklist which require investigation
- Active disease (defined as faecal calprotectin 200 or over and/or IBD control score 13 or under)
- Abnormalities detected on blood test in people with fatigue
- Irritable Bowel Syndrome or functional dyspepsia diagnosed in people with pain (by responses on checklist)
- Untreated loose stool detected in people with urgency

Secondary outcomes

- Proportion of participants for whom a clinical intervention was indicated
- Proportion of participants who declined a suggested clinical intervention at consultation
- The cost of implementing the algorithm (clinical tests or intervention and nurse/clinician time to implement the algorithm)
 The checklist (Appendix 4) also includes the following measures, which will be repeated at 3 months (Appendix 6):

- PROMIS Short Form v1.0 Fatigue 4a; 4 item validated scale to measure fatigue (14)
- PROMIS Scale v1.0 Pain Intensity 3a; 3 item validated scale to measure pain (14)
- PROMIS Scale v1.0 Gastrointestinal Bowel Incontinence 4a; 4 item validated scale to measure bowel control (15)
- IBD-Control score; 8-item self-reported score to measure disease control from the patient's perspective (13)
- EQ-5D-5L (Quality of Life measurement); a 5-item standardised measure of health (16)

Only those participants needing interventions as indicated by the algorithm, will be sent the outcome questionnaire (Appendix 6) at 3 months after return of the initial checklist and stool sample. This questionnaire will also include a free text feedback option at follow up to capture qualitative comments about the experience of completing the checklist and algorithm, and how onerous or helpful this was.

In addition, the nurse/clinician will complete the Optimisation CRF for each participant (Appendix 5), this will include number of visits or telephone contacts, all tests and results and all management initiated within the algorithm. Qualitative comments on taking the participant through the process of using the checklist and algorithm will be collected here.

Feasibility outcomes will include number consenting but then discontinuing (with reasons if possible), completion of outcome measures, completion of CRFs.

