7. DATA ANALYSIS, MANAGEMENT AND PROTECTION

7.1 Data analysis

The percentage of patients requesting help with their symptoms who report at least one treatable cause will be estimated. The percentage of patients with each treatable cause will be estimated among all those seeking help. For those receiving intervention, change in fatigue, pain and incontinence scores will be estimated with confidence intervals.

The change in generic health-related quality of life (EQ-5D-5L) from survey to end of optimisation and the cost of implementing the optimisation algorithm will be evaluated.

We will collect data on all significant health (NHS perspective) resource inputs associated with optimising medical management. This will include hospital visits, diagnostic procedures, medication. The intervention-specific cost (email, telephone contacts, and tests) will be calculated based on the records (by nurses and doctors) of their interactions with patients. Unit costs from national sources will be applied to estimate patient-level total healthcare costs.

Free text comments from participants gathered in the questionnaire at 3 months (Appendix 6) and from nurses/clinicians (Appendix 5) will be subjected to a simple thematic analysis to determine views on feasibility and any changes suggested.

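### The cost population is inconsistent: the summary and question III cost only managed participants, while the aim and the 6.2 outcome are the cost of an algorithm applied to everyone

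*Protocol*

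**What the plan says.** The protocol describes the cost analysis in several places, and they do not share one population.

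**Restricted to managed participants.** The Analysis row of the Study Summary reads "Health economics analysis to estimate (among participants undergoing medical optimisation". Section 2.2, question III, asks: "In patients starting algorithm-led management, what NHS resources are used during the implementation of the algorithm". Section 7.1 leans the same way: "We will collect data on all significant health (NHS perspective) resource inputs associated with optimising medical management".

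**No restriction.** The Objectives/Aims row of the Study Summary joins feasibility in clinical "practice and the costs incurred by the NHS, and additional" qualitative work, without naming a subset. Section 6.2 lists as a secondary outcome "The cost of implementing the algorithm (clinical tests or intervention and nurse/clinician time to implement the algorithm", again without a subset.

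**Data sources.** Section 7.1 says of the inputs: "This will include hospital visits, diagnostic procedures, medication". It then says that the intervention-specific cost, which covers email, telephone contacts and tests, "will be calculated based on the records (by nurses and doctors) of their interactions with patients". Section 6.2 states that "the nurse/clinician will complete the Optimisation CRF for each participant (Appendix 5"). Section 6 has the central research team take calprotectin results from the laboratory portal and enter them on a separate Calprotectin CRF.

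**The concern.** The algorithm is not confined to those who end up managed. Under section 3, everyone who consents and returns a checklist is sent a stool kit, and the calprotectin result is itself a step of the algorithm. Under section 1.4, a nurse or clinician reviews the checklist, the calprotectin result and the medical notes, and some participants are then found to need nothing further. They have used NHS resources within the algorithm, but they never start management, so the summary and question III leave them out.

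The reduced study is meant to concentrate on feasibility (section 4.3), and section 1.3 describes equipoise over whether patients need this medical step before self-management. A service weighing that question pays for everyone it screens. A cost drawn only from managed patients does not give that figure. It also does not match the primary outcome, whose denominator is all participants.

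**Working it through.** **Step 1. Is there a figure to reproduce?** The protocol gives no cost figure. Its only sizing figure is the 95% confidence interval width of at most 13.9% at 200 participants, which reproduces: 2 × 1.96 × √(0.25/200) = 0.1386. It plays no part here beyond supplying N = 200.

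**Step 2. Inputs.** N = 200 (section 4.3). The others are not in the documents and are assumed:
- q: share of participants with nothing found;
- S: screening cost per person (kit, laboratory test, clinician review);
- M: further cost per managed patient.

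The sum treats everyone with a finding as managed. Participants who decline management would also fall outside the restricted population and would act like a larger q.

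**Step 3. Two totals.**
- Everyone who enters the algorithm: N × S + N(1 − q) × M.
- Managed participants only, with their own screening counted: N(1 − q) × (S + M).
- Difference: N × q × S.
- Difference per managed patient: NqS / [N(1 − q)] = S × q/(1 − q).

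**Step 4. Relative size.** With r = S/M, the full cost per managed patient in units of M is 1 + r/(1 − q), and the restricted cost is 1 + r. The understatement is 1 − (1 + r)/(1 + r/(1 − q)).

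| q | Nothing found, of 200 | Managed | q/(1 − q) | Understated, r = 0.1 | r = 0.25 | r = 1.0 |
|---|---|---|---|---|---|---|
| 10% | 20 | 180 | 0.11 | 1% | 2% | 5% |
| 30% | 60 | 140 | 0.43 | 4% | 8% | 18% |
| 50% | 100 | 100 | 1.00 | 8% | 17% | 33% |
| 60% | 120 | 80 | 1.50 | 12% | 23% | 43% |

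Worked line at q = 50%, r = 0.25: full cost 1 + 0.25/0.5 = 1.50; restricted cost 1.25; 1 − 1.25/1.50 = 17%.

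**Step 5. The error can run the other way.** The full cost per person screened is S + (1 − q)M. If the restricted mean, S + M, were read as the cost of putting one person through the algorithm, it would be too high by qM. The restricted figure therefore gives neither the full cost per managed patient nor the cost per person screened.

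**Step 6. Source of the calprotectin cost.** Section 7.1 ties test costs to clinicians' records of patient contacts. The calprotectin kit is posted to the participant, analysed at one laboratory and recorded by the central team. The costing text mentions neither the kit nor the Calprotectin CRF, so the source for this item is not stated.

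**The case against.** A reader might infer more: that the calprotectin cost is left out altogether, for managed patients too. The protocol does not support that. Section 7.1 promises all significant inputs and lists diagnostic procedures and tests. Section 6.2 costs clinical tests and has the Optimisation CRF hold all tests and results. Calprotectin is a step of the algorithm, and no text excludes it. The sentence on nurse and doctor records governs only the intervention-specific part of the cost. What remains is an unnamed source, not a shown omission.

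The other side has further points.

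- **The restricted population has a rationale.** Only participants needing intervention receive the 3-month questionnaire, so costs and EQ-5D-5L change would be reported in the same people. That is a good reason to report the subset. It does not make the subset's cost the cost of implementing the algorithm.
- **Costing detail may sit in an analysis plan that is not shown.** This holds for unit costs and methods. The population, however, is set in the protocol itself, and set in two ways.
- **The share with nothing found may be low.** Participants are symptomatic and asked for help, and the primary composite is broad. At q = 10% the understatement is 1% to 5% over the values of r above. This stands, and it limits what can be said about size.
- **Some handling is done by the central research team and is not clearly an NHS cost.** This stands too, so the point should rest on the kit, the laboratory test and clinician review. A call or visit is only a possibility under section 3 and should not be assumed for everyone.

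**Conclusion.** The concern holds as an inconsistency in the cost population. The summary and question III restrict costing to managed participants; the aim and the section 6.2 outcome do not. Under the restricted text, the calprotectin test and clinician review of participants with nothing found go uncosted, and the aim of determining the NHS cost of the checklist and algorithm is not met.

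The understatement per managed patient is S × q/(1 − q), about 0.11 S at q = 10% and 1.5 S at q = 60%. Both S and q are assumptions, so no amount in pounds can be given. The effect is minor if nearly everyone goes on to management and substantial if about half do not. The missing reference to the Calprotectin CRF is a secondary matter of clarity. The point should be corrected, since it bears on the cost conclusion and is cheap to resolve.

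**What to change.** - In the Study Summary, section 2.2 question III and section 7.1, set the cost population as all participants who enter the algorithm.
- Report the cost per participant screened, with managed participants as a stated subset. The subset keeps the link with EQ-5D-5L change.
- In section 7.1, state that the stool kit, the laboratory calprotectin test and clinician checklist-review time are costed, and name the Calprotectin CRF and the Optimisation CRF as sources.

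The cost is a little more costing work. Most of the data are already planned, since the Optimisation CRF is completed for every participant and the Calprotectin CRF records the test results. One gap is possible: the contents that section 6.2 lists for the Optimisation CRF do not include review time. If the form itself (Appendix 5, not shown) does not record it either, an assumed duration will be needed, declared and varied over a range.

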If nothing further needs to be done according to the algorithm (patient is in remission and no further tests or management is indicated), the participant will be informed of this, thanked for their participation by letter/email (Appendix 14). They will be offered the RCT if they have consented for further research contact and are eligible for the RCT. If active IBD disease or any other of the issues in the IBD-BOOST algorithm are identified, the IBD nurse/clinician will initiate management based on the algorithm.

If a participant is clinically unwell, with a plan to change their IBD management at the time of their checklist being reviewed, their study participation should be paused. The participant should be informed of this pause in their participation via email/letter (Appendix 15) and a new checklist should be re-sent to them 6 months later via post or email. This new checklist should then be used to follow the algorithm. Participants will also complete a new faecal calprotectin sample at the same time as completing the new checklist.

Participants will have completed measures of symptom severity and IBD control when completing the checklist. If intervention is indicted by the algorithm, they will complete the patient reported outcome questionnaire (Appendix 6) at 3 months after return of both the checklist and faecal calprotectin test (only for those for whom the checklist indicates an abnormality which the algorithm addresses). Nurses will keep a record of their interactions with patients (phone calls, emails or clinic visits), tests ordered, results and interventions using a case report form (Appendix 5).

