6. DATA COLLECTION

The checklist (Appendix 4) and outcome measures at 3 months (Appendix 6) will be selfadministered. Participants will be invited to complete these through an online link provided or via paper copies sent to the study research team and stored at King's College London or LNWUH Trust. Data from the online version will be directly inputted into the database by participants. Paper copies received in the post will be inputted manually into the database by the research team.

Results for calprotectin tests on stool samples provided by the participant will be accessed by the central research team on King's College Hospital laboratory's secure results portal and uploaded on to the study database on the Calprotectin CRF (Appendix 11). Once the checklist and algorithm data are both available the participant's usual care clinical site will have four weeks to review and contact the participant.

If the checklist indicates an abnormality which the algorithm addresses, the participant will be sent the patient reported outcomes questionnaire (Appendix 6) at 3 months after the IBD nurse has reviewed the checklist. The questionnaire contains measures on symptom and IBD control repeated from the checklist and measures of quality of life also used in the IBD-

BOOST survey. Those who require a 3 month follow up will be sent this via email/letter and will be sent up to 2 reminders by email or text message for non-responders (Appendix 10).

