6.3 IBD-BOOST Study Schedule

IBD-BOOST OPTIMISE		Within 1 week of completing checklist	Within 10 weeks of consent/ 2 weeks of trial team receiving the calprotectin result	Within 4 weeks of checklist and calprotectin data sent to clinical team	Within 3 months of checklist and calprotectin result reviewed	3 months after checklist and calprotectin result reviewed	Before study closure
Time Point	Т0	T1	T2	Т3	T4	T5	T6
Screening and invite sent	Х						
Participant Information Sheet	Х						
Consent Form	Х						
Checklist	Х						
Stool sample kit sent to participant		Х					
Calprotectin result received and uploaded by central research team			X				
Checklist and calprotectin result reviewed by patient's local IBD team				Х			
Medical Management Optimisation (if required)					X		
Participant reported Outcome Questionnaire completed (only if management provided)						X	
Clinician Qualitative Process Evaluation Interviews							Х

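### Follow-up closes 90 days after the last recruitment date, but the protocol's own schedule allows up to 27 weeks from consent to the 3-month outcome, so late recruits are not assured of one

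*Protocol*

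**What the plan says.** The Study Summary gives a start of 1 June 2019, an end of "31 st December 2022" and a follow-up end of "31 st March 2023", with a recruitment duration of 43 months and a total of 46 months. All three dates are labelled as proposed.

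The schedule in section 6.3 sets these limits:

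- T2, calprotectin result uploaded: "Within 10 weeks of consent/ 2 weeks of trial team receiving the calprotectin result".
- T3, review by the local IBD team: "Within 4 weeks of checklist and calprotectin data sent to clinical team".
- T5, outcome questionnaire: "3 months after checklist and calprotectin result reviewed".

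The text gives two starting points for the 3 months. Section 6 agrees with the schedule and sends the questionnaire "at 3 months after the IBD nurse has reviewed the checklist". Section 3 places it "at 3 months after return of both the checklist and faecal calprotectin test", and section 6.2 does the same. Sections 3, 6.2 and 6.3 restrict the questionnaire to participants for whom the algorithm leads to intervention.

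Section 3 also pauses a participant who is clinically unwell with a change of IBD management planned when the checklist is reviewed: "a new checklist should be re-sent to them 6 months later via post or email". A new stool sample goes with it, and the new checklist is the one the algorithm then uses.

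**The concern.** The gap between the end of recruitment and the end of follow-up equals the last interval of the schedule and nothing more. It leaves no time for the stool kit to be posted and returned, for the laboratory result, or for the site's review, all of which come before the 3-month point under at least one of the protocol's two definitions. The visible text sets no earlier last-consent date and no rule for participants still in progress on 31 March 2023.

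If the dates are followed as written, some late recruits have no 3-month outcome for an administrative reason, and a participant paused late in the study has no usable second assessment. Pausing depends on being unwell, so that second loss is related to disease state.

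**Working it through.** **Reproducing the stated durations.** June to December 2019 is 7 months, and 2020 to 2022 adds 36, giving 43. January to March 2023 adds 3, giving 46. Both figures reproduce, so 31 December 2022 is the end of recruitment. From there to 31 March 2023 is 90 days, or 12.9 weeks.

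**Longest path without a pause.** The inputs are the section 6.3 limits, with 3 months taken as 13 weeks. I assume that results reach the site on the day they are uploaded.

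- Anchored on review (sections 6 and 6.3): 10 + 4 + 13 = 27 weeks.
- Anchored on return of checklist and sample (sections 3 and 6.2): at most 10 + 13 = 23 weeks, using the T2 limit as an upper bound for the return.

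For consent on 31 December 2022:

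| Step | Weeks from consent | Date |
|---|---|---|
| Calprotectin result (T2) | 10 | 11 March 2023 |
| Review (T3) | 14 | 8 April 2023 |
| Questionnaire, return anchor | 23 | 10 June 2023 |
| Questionnaire, review anchor (T5) | 27 | 8 July 2023 |

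With no delay at all before the data reach the site, the review window and 3 months still give 4 + 13 = 17 weeks, or 29 April 2023. The stated end is met only if the 3-month clock starts on the day of consent. That cannot happen, because the kit is posted after the checklist is completed.

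**Latest consent assured of a 3-month outcome by 31 March 2023.** Counting back 27 weeks gives 23 September 2022. Counting back 23 weeks gives 21 October 2022.

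**How many consents.** The protocol gives no accrual curve, so even accrual is an assumption: 200 / 43 = 4.65 a month.

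- After 23 September 2022: 99 days = 3.25 months; 3.25 × 4.65 = about 15.
- After 21 October 2022: 71 days = 2.33 months; 2.33 × 4.65 = about 11.
- If consent to review takes 8 weeks (assumption) instead of 14: 1.84 months × 4.65 = about 9.

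These are consents, not lost questionnaires. The share needing intervention is not given. At 25%, 50% or 75% (assumptions), the 15 become about 4, 8 or 11.

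**Primary outcome without a pause.** Review at week 14 passes 31 March 2023 only for consents after 23 December 2022. That is 8 days, or 8 / 30.44 × 4.65 = about 1 participant. Blood-test abnormalities in people with fatigue are one primary component, and section 6.3 lets optimisation run for up to 3 months after review. Such results could therefore arrive after closure for consents from late September 2022 onward.

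**Paused participants.** At the limits, the pause is decided at review (week 14), the checklist is re-sent 26 weeks later, and the 27-week path runs again (taking the same limits to apply from the re-send): 14 + 26 + 27 = 67 weeks. Counting back from 31 March 2023, only consents by about 17 December 2021 are sure to finish. A last-day recruit who is paused could run to 13 April 2024.

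**The case against.** The windows are upper limits, and most participants will move faster. The dates are proposed dates, and nothing says that a questionnaire due after 31 March 2023 is refused or discarded. The Gantt chart in section 10.1 has a row for the follow-up questionnaire and columns to the end of 2023, but its bars are not legible in the available text, so it can neither confirm nor correct the dates. Even accrual is a weak assumption when section 4.3 reports that Covid-19 cut the target from 500 to 200. All of this stands, and it limits what can be said about size. It does not reconcile the dates, because a last-day recruit misses the stated end under either anchor even at good speed.

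Three stronger readings are tempting, and the protocol does not support them:

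- **That about 15 participants lose their outcome.** Fifteen is a ceiling on late consents with every limit used in full. Those with no intervention have no questionnaire to lose.
- **That the primary proportion suffers as much as the change analyses.** Four of its five components come from the checklist, the calprotectin and IBD-Control results, or the review. Late blood results matter only for a participant with fatigue and no other positive component.
- **That 8 July 2023 is the one date the protocol requires.** It follows from the review anchor; the other anchor gives 10 June 2023.

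**Conclusion.** The point holds as a timeline inconsistency of modest size. The stated follow-up covers only the last interval of the schedule, and participants consenting after about 23 September 2022 (21 October under the other anchor) are not assured of a 3-month outcome. The effect falls mainly on the symptom-score and EQ-5D-5L change analyses among those needing intervention. At most about 15 consents are involved, under even accrual and full use of the limits, with fewer questionnaires lost.

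The primary outcome is exposed in three narrow places: about the last week of consents, blood results obtained late in optimisation, and paused participants. The protocol gives no pause rate, so the last cannot be sized. The conclusion that the dates do not fit depends on neither the accrual assumption nor the choice of anchor; only the counts and cut-off dates do.

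**What to change.** 1. Move the follow-up end to at least 8 July 2023. This lies within the programme end planned for November 2023 in section 7.2. Alternatively, keep the closing date and set a last-consent date about 27 weeks before it. Some allowance for the questionnaire reminders in section 6 would be sensible.
2. Reconcile the two starting points for the 3 months (sections 3 and 6.2 against sections 6 and 6.3), and derive the closing date from the one retained.
3. State how participants whose pause cannot be completed before closure are counted in the primary and change analyses. A later date does not settle this, since a 67-week path from the last recruitment day runs to April 2024. The rule has to agree with section 3. Simply falling back on the first checklist would conflict with its instruction that the new checklist is used, unless section 3 is changed too.

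The cost is an amendment to the dates, about 3 more months of questionnaire collection, and a later data lock. The last-consent alternative avoids the extra collection but gives up the late recruits.
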